9.1 Data Presentation

The actual clock time for dosing start and end and the actual clock time for each collection time for the PD samples will be recorded using electronic data capture. For all sampling times, the actual sampling times will be calculated as the difference between the sample collection actual clock time and the actual clock time of dosing end. The actual post-dose sampling times, expressed in hours and rounded off to three decimal digits, will be used to calculate the PD parameters. Pre-dose samples will always be reported as “0.000”, regardless of the time difference.

9.2 Plasma PD Sampling Schedule

A total of 14 blood samples will be collected in each cohort for PD analysis: pre-dose (baseline) and 1, 4, 6, 12, 24, 36, 48, 96, 168, 336, 504, 672, and 1416 hours post-start of infusion.

9.3 Plasma PD Parameters

Individual and mean plasma concentration versus time curves will be presented for both linear and semi-log scales for normalized and actual FAM19A5.

Normalized and actual plasma FAM19A5 and changes from baseline Δ FAM19A5, along with PD parameters will be presented in data listings and summarized in tables by treatment, using descriptive statistics (n, arithmetic mean, geometric mean, SD, CV%, min, max, and median).

The following PD parameters will be calculated for plasma normalized and actual FAM19A5:

Parameter	Definition
AUEC _{0-t}	area under the PD effect versus time curve from time zero until the last measurable timepoint
E _{max}	maximum observed effect
TE _{max}	time of E _{max}

AUEC_{0-t}, will be calculated using the linear trapezoidal method (linear up log down).

9.4 CSF PD Sampling Schedule

Subjects included in Cohorts 5 through 8 will have one CSF sample collected, via lumbar puncture, at one of the following timepoints: 24, 36, 168, or 336 hours post-start of infusion.

All FAM19A5 concentrations in CSF will be listed, as well as the ratio of FAM19A5 in serum to FAM19A5 in CSF at the applicable time-matched timepoint, i.e. serum FAM19A5 /CSF

This document is confidential.

FAM19A5 at time xx hrs.

This document is confidential.

10. Immunogenicity Analyses

All immunogenicity summaries, listings, and analysis will be conducted on the immunogenicity population. Listings will be provided for the immunogenicity population.

The number and percentage of subjects who develop detectable ADA and NAb will be summarized. The main PK parameters will be summarized by dose level and category of ADA status (at least one positive/negative). A listing showing immunogenicity test results from each three-tiered approach will be presented by treatment and visit.

The ADA assay will follow a three-tiered approach consisting of (i) screening assay, (ii) confirmatory assay, and (iii) titration. Samples that are “confirmatory” in the screening assay will undergo further testing in the confirmatory assay to determine if subjects are true positive. The overall ADA assay result will be “positive” or “negative”. For further characterization, the antibody level will be assessed by titration in confirmed positive samples. The confirmed positive samples in the ADA assay will be analyzed further to conduct a NAb assessment. The test outcome for NAb assay will be “positive” or “negative”.

The results of the final ADA assay and the NAb assay will be summarized. The number and percentage of subjects will be provided by dose level and visit. The descriptive statistics of ADA titration results for each treatment group will be presented by visit. The number and percentage of subjects with at least one positive ADA assay and the number and percentage of subjects with at least one positive NAb assay status after study drug administration (including unscheduled visit and Study Exit visit) will also be presented in a table. Vertical bar plots with percentage of subjects with positive ADA results will be provided.

If positive ADA positive results are available, an overall summary table of TEAE will be provided for ADA positive vs negative results.

Boxplots will present PK levels for each dose level by ADA status.

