In terms of immunogenicity, almost all samples were found to be negative to ADA during the screening assay, with the exception of 5/219 samples (2.3%) for which positivity was detected, with signals very close to the cut-point. Three of them belong to the control group and the remaining positive samples were collected at pre-test. Therefore, they were not considered related to the administration of test item.¹

For all samples where the NS101 concentrations were $> 1.25 \mu g/mL$ (drug tolerance threshold defined during the method validation) and that were determined to be immunogenicity negative, drug interference with the detection of anti-NS101 antibodies cannot be excluded.¹

The clinical observation results revealed that:

- All animals survived until scheduled necropsies.
- There were no test item-related effects on clinical signs, food consumption, ophthalmology, urinalysis or macroscopic and microscopic examinations.
- Body weight gain was minimally to slightly higher over the treatment period in males and females at 150 and 300 mg/kg/dose.
- Clinical pathology findings at the end of the treatment period consisted in higher lymphocyte counts (up to 2-fold) in females at ≥ 50 mg/kg/dose and males at 300 mg/kg/dose; higher reticulocyte counts in females at 300 mg/kg/dose (+42%); shortened activated partial thromboplastin and prothrombin times (up to -19%) in females

at \geq 50 mg/kg/dose and males at \geq 150 mg/kg/dose; decreased albumin to globulin ratio (up to -12%); lower cholesterol levels in females at \geq 50 mg/kg/dose (up to -27%) and higher triglyceride concentrations in females at \geq 150 mg/kg/dose (up to +83%).

- Organ weight changes included a decrease in the heart weight in males at 300 mg/kg, and an increase in the liver weight in males and females at ≥ 150 mg/kg/dose, without histopathological correlations. No other test article-related organ weight changes were noted. There were also no other indications of stress, which could otherwise possibly explain increased weight of the adrenal gland.
- Based on the clinical dosing planned in the upcoming first in human trial as a single dose, the repeated dose observation will not be clinically significance.¹

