NS101 of 300 mg/kg/dose at week 8 displayed neutralizing ADA in all tested cynomolgus monkeys. Nevertheless, this led to no immunologically significant findings because the microscopic assessment showed no observed immunogenicity and/or immune complex deposition during the recovery period (Table 4).¹

Table 4. Summary Of ADA Response And Consequence

	Week 4 (A	At the end of	final treatme	nt)	Week 8 (4 wee	eks after the	last injectior	1)
Dose level (mg/kg)	Tested positive	Significant titer elevation	Positive neutralizing effect	n	Tested positive	Significant titer elevation	Positive neutralizing effect	n
0	1	ND	ND	10	1	ND	ND	4
30	2	ND	ND	6	NA	NA	NA	0
90	1	1	1	6	NA	NA	NA	0
300	1	1	1	10	4	4	4	4

The toxicokinetic results are described in the Investigator's Brochure.¹

Due to the important presence of ADAs, particularly NAbs, the PK and safety data from this study were not used for study design of the upcoming FIH study.

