3.6 Subject Withdrawal and Replacement

Subjects who withdraw, or are withdrawn, from the study for safety and tolerability reasons after

This document is confidential.

dosing will not be replaced. However, subjects who withdraw or are withdrawn from the study after dosing for reasons other than safety and tolerability, may be replaced. The total number of subjects dosed (including potential replacement subjects) will remain within a maximum of 10 subjects per cohort.

This document is confidential.

4. Endpoints

- Primary endpoints:
 - Incidence, nature, relatedness, and severity of AEs.
 - Changes in vital signs measurements, physical examination, clinical laboratory test findings, and 12-lead electrocardiogram (ECG) results.
- Secondary endpoints:
 - Serum PK parameters for NS101 will include the following:
 - area under the concentration-time curve, from time zero to 24-hours (AUC_{0-24})
 - area under the concentration-time curve from time zero until the last observed concentration (AUC_{0-t})
 - area under the concentration-time curve from time zero to infinity ($AUC_{0-\infty}$)
 - maximum observed concentration (C_{max})
 - time when the maximum concentration is observed (T_{max})
 - terminal elimination half-life ($T_{1/2 el}$)
 - elimination rate constant (K_{el})
 - apparent body clearance (Cl)
 - apparent volume of distribution (V_z)
 - Concentrations of NS101 in CSF for Cohorts 5 to 8
 - Serum to CSF ratio of NS101 concentrations
 - Immunogenicity of NS101, measured as the number and percentage of subjects who develop detectable anti-drug antibody (ADA) and neutralizing antibody (NAb)
- Exploratory endpoints:
 - Effect (E): variation of level of FAM19A5 ($\Delta FAM19A5$) following administration of NS101:
 - PD: Change in baseline of FAM19A5 levels
 - The following PD parameters in plasma:
 - $AUEC_{0-t}$
 - maximal observed effect (E_{max})
 - time of maximal observed effect (TE_{max})
 - Concentrations of FAM19A5 in CSF

This document is confidential.

5. Analysis Populations

All subjects' inclusion status into each analysis population will be determined after database lock.

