5.7 Immunogenicity Population

The immunogenicity population will include all subjects who have received any amount of NS101 and have at least one post-dose ADA/NAb measurement.

This document is confidential.

6. General Aspects for Statistical Analysis

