6.1 General Methods

SAS for Windows, Release 9.4, software will be used to perform all data analyses.

All data in the database will be presented in the data listings. Unless otherwise stated, all listings will be sorted by randomized cohort, subject number, and assessment date and time. For the purposes of the summary tables, all subjects randomized to placebo will be pooled into a single placebo group.

The following labels for treatment will be used on all tabulations where the results are displayed by treatment, in the following order:

- All Placebo
- NS101 0.25 mg/kg
- NS101 0.75 mg/kg
- NS101 1.50 mg/kg
- NS101 3.0 mg/kg
- NS101 6.0 mg/kg
- NS101 12.0 mg/kg
- NS101 24.0 mg/kg
- NS101 48.0 mg/kg

6.2 Summary Statistics:

Unless otherwise stated, continuous variables will be summarized using the number of observations (n), and the statistics mean, median, standard deviation (SD), minimum (min) and maximum (max). The min and max values will be presented to the same number of decimal places as recorded in the case report form (CRF), median will be presented to one more decimal place than the raw data and the mean and SD will be presented to two more decimal places than the raw data. Summaries of change-from-baseline variables will include only subjects who have both a baseline value and corresponding value at the timepoint of interest. Categorical variables will be summarized with frequency counts and percentages. Percentages will be rounded to one decimal place, with the denominator being the number of subjects in the relevant population, unless otherwise stated.

For the serum and CSF PK and PD data, the data will be rounded to two decimal places in the listings, except for the following situations:

- Elimination rate constant (K_{el}) data: rounded off to four decimal digits
- PK parameters related to time, such as T_{max} , $K_{el\ Lower}$, and $K_{el\ Upper}$, will be reported with the same precision as the actual sampling time: rounded off to 3 decimal digits
- Concentration versus time data, as well as C_{max} : reported as they appear in the corresponding dataset

Summary statistics include the geometric mean (two decimal places) and coefficient of variation (CV)% (two decimal place). The geometric mean and CV% will not be calculated for T_{max} , $T_{1/2\ el}$, and K_{el} .

This document is confidential.

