10.1 Immunogenicity Sampling Schedule

A total of 6 immunogenicity blood samples will be collected: pre-start of infusion and at 96, 336, 504, 672, and 1416 hours post-start of infusion.

This document is confidential.

11. Safety

Safety and tolerability analysis will be performed for all subjects in the Safety Population. Safety and tolerability data will be reported using descriptive statistics. No inferential statistical analysis of safety data is planned.

Safety and tolerability to NS101 will be evaluated through the assessment of AEs (i.e., seriousness, severity, relationship to the study drug, outcome, duration, and management), vital signs, 12-lead ECG, clinical laboratory parameters, weight, and physical examination. treatment-emergent adverse events (TEAEs) will be tabulated by study treatment. Changes from baseline values in vital signs, ECG, and clinical laboratory parameters tabulated by study treatment will be evaluated.

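### The SAP classes every ADA result as positive or negative without regard to serum NS101, so negatives that the drug may have masked count as negative, and no inconclusive category exists.

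*SAP*

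**What the plan says.** Immunogenicity is a secondary endpoint (SAP section 4), "measured as the number and percentage of subjects who develop detectable anti-drug antibody (ADA) and neutralizing antibody (NAb".

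SAP section 10 describes a three-tier assay and then says: "The overall ADA assay result will be “positive” or “negative". The subject-level status is carried into the PK tables: "The main PK parameters will be summarized by dose level and category of ADA status (at least one positive/negative". The TEAE overview by ADA result and the PK boxplots rest on ADA status too.

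No drug-level condition appears elsewhere. The immunogenicity population (SAP section 5.7) needs NS101 dosing and subjects who "have at least one post-dose ADA/NAb measurement". Percentages (SAP section 6.2) are taken "with the denominator being the number of subjects in the relevant population, unless otherwise stated". Protocol section 13.5 has no such rule either and leaves the detail to the SAP.

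ADA samples are taken (SAP section 10.1) "pre-start of infusion and at 96, 336, 504, 672, and 1416 hours post-start of infusion". SAP section 8.2 lists a serum PK sample at each of those times.

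The protocol's nonclinical summary raises the issue itself. In the 4-week rat study (section 5.2.3.2), for negative samples with NS101 above 1.25 µg/mL, "drug interference with the detection of anti-NS101 antibodies cannot be excluded".

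**The concern.** An ADA assay can miss antibody when circulating drug exceeds its tolerance. NS101 is expected to be long-lived and is given over a 192-fold dose range (0.25 to 48 mg/kg), so the post-dose samples will differ widely in how much drug they contain. A negative in a low-dose subject and a negative in a 48 mg/kg subject may not mean the same thing, but the SAP treats them alike.

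Two outputs are at stake. First, any masking pulls observed incidence down, so a flat or falling ADA rate across doses could be an artefact. With 6 active subjects per cohort, one misclassified subject moves a cohort's incidence by 1/6, about 17 percentage points. Second, masked subjects would sit in the negative group when PK and TEAEs are compared by ADA status, which blurs the contrast those tables are meant to show.

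**Working it through.** The plan gives no figure for this point. The check asks how many of the five post-dose ADA samples would contain NS101 above a given tolerance.

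**Inputs**
- Doses: 0.25, 0.75, 1.5, 3, 6, 12, 24, 48 mg/kg. Times: 96, 336, 504, 672, 1416 h.
- Initial concentration per mg/kg (k). Low: 31/12 = 2.58 µg/mL, from the expected human Cmax of about 31 µg/mL at 12 mg/kg (protocol 5.4.1). High: 20 to 30 µg/mL, from 200 to 300 µg/mL after 10 mg/kg in rats and monkeys (protocol 5.2.1.2). The cytokine conversion in protocol 5.4.1 (10 µg/mL at 0.375 mg/kg) gives 26.7, inside this range.
- Half-life: 329.9 h, from mice and described as potentially expected in humans (protocol 8.1); 181.0 to 281.6 h (single-dose rats, 5.2.4.2); 78.0 h (low end, repeat-dose rats, 5.2.4.3).
- Tolerance: 1.25 µg/mL is the only value in the documents and belongs to the rat assay. 50 µg/mL is added as an assumed, more tolerant assay.

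**Formula:** C(t) = k × dose × 0.5^(t / half-life). This is dose-linear and mono-exponential; it ignores distribution and any faster clearance caused by ADA.

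**Check on dose-linear scaling.** Protocol 5.2.1.2 scales 200 to 300 µg/mL by 1/33 to 6 to 9 µg/mL. 200/33 = 6.1 and 300/33 = 9.1, so it agrees.

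**Samples (of 5) above 1.25 µg/mL, half-life 329.9 h**

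| k | 0.25 | 0.75 | 1.5 | 3 | 6 | 12 | 24 | 48 mg/kg |
|---|---|---|---|---|---|---|---|---|
| 2.58 | 0 | 1 | 3 | 4 | 4 | 5 | 5 | 5 |
| 20 | 3 | 4 | 5 | 5 | 5 | 5 | 5 | 5 |
| 30 | 4 | 4 | 5 | 5 | 5 | 5 | 5 | 5 |

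**48 mg/kg across half-lives**

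| k | Half-life (h) | Day 60 level (µg/mL) | Above 1.25 | Above 50 |
|---|---|---|---|---|
| 2.58 | 181 | 0.55 | 4 | 1 |
| 2.58 | 281.6 | 3.8 | 5 | 2 |
| 2.58 | 329.9 | 6.3 | 5 | 2 |
| 20 | 181 | 4.2 | 5 | 4 |
| 20 | 329.9 | 49.0 | 5 | 4 |
| 30 | 181 | 6.4 | 5 | 4 |
| 30 | 329.9 | 73.5 | 5 | 5 |
| 2.58 | 78 | below 0.01 | 3 | 1 |
| 30 | 78 | below 0.01 | 4 | 2 |

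Worked example, k = 2.58, 181 h, 96 h sample: 2.583 × 48 × 0.5^(96/181) = 124 × 0.692 = 85.9 µg/mL.

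**Reading**
- For half-lives of 181 to 330 h, 4 to 5 of 5 samples at 48 mg/kg exceed 1.25 µg/mL and 1 to 5 exceed 50 µg/mL.
- With 78 h, Day 60 is below 1.25 µg/mL at every dose, even with k = 30.
- The count above tolerance never falls as dose rises. In a dose-linear model that holds by construction, so it gives a direction and not a size. When tolerance is low and exposure high, middle doses are exposed as well and the gradient flattens.
- At 48 mg/kg and 329.9 h, the 96 h level is about 101 µg/mL (k = 2.58) or 785 to 1,177 µg/mL (k = 20 to 30). A clinical tolerance above those levels would remove the issue in that scenario.

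**The case against.** **The endpoint concerns detectable antibody, and the SAP never calls its negatives true negatives.** That is correct. But the SAP does label these subjects negative, counts them in the denominator and compares PK and TEAEs against them.

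**A subject is positive if any post-dose sample is positive, including study exit.** This has force. Masking at early visits alone does not make a subject negative. If elimination is fast, or if ADA itself clears the drug, Day 60 could recover most subject-level positives. Visit-level percentages would still be exposed.

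**The human assay's tolerance is in neither document and may be high.** This stands and prevents any statement of size. It does not remove the need for a rule, which can refer to the validated value.

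**A careful reader could match the listed ADA results to the listed serum concentrations.** True, but the summary tables would still carry the two-way status.

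**The monkey data.** A reader might infer that these show masking: in protocol Table 4, 1 of 10 animals at 300 mg/kg was positive at Week 4 and 4 of 4 at Week 8, and the text says "NS101 of 300 mg/kg/dose at week 8 displayed neutralizing ADA in all tested cynomolgus monkeys". The documents do not support that inference. Late antibody onset explains the same pattern. Nor was drug necessarily gone by Week 8. Taking the last 300 mg/kg dose alone, with k = 20 to 30 and half-lives of 181 to 281.6 h, 6,000 × 0.5^(672/181) to 9,000 × 0.5^(672/281.6) leaves about 460 to 1,700 µg/mL. So either that assay found ADA despite drug, or ADA had cleared the drug.

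**Conclusion.** The gap is real: the SAP has no rule linking an ADA negative to the concurrent serum NS101 level, although the protocol recognises the problem in rats and the PK samples needed for a rule are already scheduled. Any masking would bias observed incidence downward and contaminate the negative group in the PK and TEAE tables. Exposure to masking does not fall with dose.

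The size of the bias is not known. It depends on the human assay's tolerance, the true ADA rate and the chance of masking, none of which is given. The modelled counts rest on a simple decay model and on exposure figures that differ about 8- to 12-fold per mg/kg (20/2.58 to 30/2.58).

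A reader might infer that high-dose ADA incidence will certainly be understated, or by how much. The documents do not support either: a tolerant assay or a short half-life would leave subject-level incidence largely intact. This is a change that should be made for a descriptive secondary endpoint; it does not touch the primary safety analysis.

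**What to change.** In SAP section 10:

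1. Refer to the clinical ADA assay's validated drug tolerance, by value or by citing the validation report.
2. Pair each ADA result with the time-matched serum NS101 concentration.
3. Report a negative sample with NS101 above tolerance as inconclusive.
4. Define subject status. Positive: any post-dose sample is positive. Negative: none is positive and a pre-specified late sample (for example the last available) is at or below tolerance. Inconclusive: otherwise.
5. Keep the planned incidence on all subjects as the main figure. Add the inconclusive count per dose and visit, and incidence excluding inconclusive subjects as a sensitivity figure. The exclusion should not be the main analysis: it removes negatives but never positives, so at a high dose it could drive incidence to 100% or to 0/0.
6. Show inconclusive as its own group in the PK and TEAE tables by ADA status.

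The cost is SAP wording and one merge of PK and ADA data, with no new samples. The downside is that fewer high-dose subjects will carry a negative label, which thins cells that already hold at most about six subjects. If the tolerance proves high, the new category stays empty and nothing is lost.

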5.4.3 Rationale for the Study Population

A male healthy volunteer population has been selected for the study because healthy subjects with no concomitant diseases and using no concomitant medications represent a homogenous population allowing for proper evaluation of the safety, tolerability, and PK of a drug without confounding factors.

No reproductive studies have been conducted in NS101. Since risks to a developing foetus or reproductive effects are not known, only male subjects will be included in the study. Furthermore, non-vasectomized male subjects with a female partner of childbearing potential will be required to use an appropriate method of contraception, and will be restricted from sperm donation.

6. Objectives

Primary objective:

To assess the safety and tolerability of NS101 following IV administration of single ascending doses in healthy subjects.

Secondary objectives:

- To characterize the PK profile of NS101 in serum and NS101 concentrations in CSF following single IV infusion doses in healthy subjects.
- To characterize the PD profile of NS101 through FAM19A5 in plasma and FAM19A5 concentrations in CSF following single IV infusion doses in healthy subjects.
- To evaluate the immunogenicity profile of NS101.

7. Study Endpoints

Primary endpoints:

- Incidence, nature, relatedness, and severity of AEs.
- Changes in vital signs measurements, physical examination, clinical laboratory test findings, 12-lead-ECG.

Secondary endpoints:

- Serum PK parameters for NS101 will include: AUC_{0-24} , AUC_{0-t} , AUC_{inf} , C_{max} , T_{max} , $T_{\frac{1}{2}}$ el, K_{el} , Cl, and V_z .
- Concentrations of NS101 in CSF.
- Serum to CSF ratio of NS101 concentrations.
- Immunogenicity of NS101, measured as the number and percentage of subjects who develop detectable ADAs and NAbs.

[figure not shown]
Exploratory endpoints:

- Effect (E): variation of level of FAM19A5 (Δ FAM19A5) following administration of NS101:
 - o PD: Change in baseline of FAM19A5 levels
 - o PD parameters in plasma: AUEC_{0-t}, E_{max} , and TE_{max} .
 - o Concentrations of FAM19A5 in CSF.

8. Study Design

This will be a single center, Phase 1, double-blind, randomized, placebo-controlled, sequential SAD study (Figure 9). The study will consist of **8** cohorts (Cohorts 1 to **8**).

Figure 9. Study Diagram

8.1 Design for Cohorts 1 to 8

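### SAP section 10 never defines who 'develops' ADA or NAb, and its only subject-level count ignores the pre-dose result

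*SAP*

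**What the plan says.** Protocol section 7 measures immunogenicity as the "number and percentage of subjects who develop detectable ADAs and NAbs", and SAP section 4 uses the same wording. SAP section 10 carries it into the analysis: "The number and percentage of subjects who develop detectable ADA and NAb will be summarized". No sentence in either document says what a subject's results must look like for him to have developed antibody. Protocol 13.5 leaves the detail to the SAP.

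Later in section 10 the SAP adds a subject-level count: "The number and percentage of subjects with at least one positive ADA assay", together with those having "at least one positive NAb assay status after study drug administration (including unscheduled visit and Study Exit visit". I read the post-dose window as applying to both ADA and NAb. On a stricter parse it attaches to NAb only, and the ADA count then has no time limit.

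The other planned outputs in section 10 are:
- ADA and NAb counts by dose level and visit, titer statistics by visit, and a listing of each assay tier by treatment and visit;
- the main PK parameters by dose level and ADA status, where one positive result suffices and no time window is given (Protocol 13.5 has the same category), with boxplots by ADA status;
- an overall TEAE table for ADA-positive against ADA-negative results, with status not defined.

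Samples are taken "pre-start of infusion and at 96, 336, 504, 672, and 1416 hours post-start of infusion" (SAP 10.1). The immunogenicity population (SAP 5.7) is NS101 recipients with at least one post-dose result. It sets no requirement on the pre-dose result.

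**The concern.** To develop antibody is a change from before dosing to after it. The one rule the SAP writes down looks only at the after. A man who is reactive before his infusion and still reactive at 96 hours satisfies it, although nothing in his results has changed.

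Elsewhere the SAP does tie outcomes to the pre-dose state. FAM19A5 change is taken from the Day 1 pre-dose sample (section 9), and an AE is treatment-emergent only if it starts on or after dosing (section 11.2). The general baseline definition in section 6.3 would supply a pre-dose ADA value, but no rule in section 10 refers to it.

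Three things are at stake. The dose-level incidence rests on six active subjects, so one misclassified man is visible. ADA status also splits the TEAE and PK summaries. And because the population holds NS101 recipients only, these tables give no placebo background rate, which leaves each subject's own pre-dose sample as the only planned control. If the rule stays open, the treatment of pre-dose positives, titer rises and missing pre-dose samples will be settled after the results are known.

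**Working it through.** The plan states no ADA rate, power or alpha for this endpoint, so there is no figure to reproduce. The check has two parts: trace result patterns through the written rules, then size the effect.

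**Step 1. Result patterns against the rules.**

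| Pre-dose ADA | Post-dose ADA | Post-dose count (SAP 10) | PK-by-ADA status (no time window) | Developed ADA? |
|---|---|---|---|---|
| negative | positive | counted | positive | yes |
| positive | positive, no titer rise | counted | positive | no |
| positive | positive, titer rise | counted | positive | boosted, if a rise is defined |
| positive | all negative | not counted | positive on a literal reading | no |
| missing | positive | counted | positive | cannot be told |

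The second row is the central problem. The fourth shows that the PK status is looser than the incidence count. The third and fifth show what else is undefined: no titer rise is set, and section 6.4 does not impute missing data.

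**Step 2. Size per subject.** There are 6 active subjects in each of 8 cohorts (SAP 3.3), so 8 × 6 = 48 active, before any replacements. One subject who is positive before dosing and remains positive adds:
- 1/6 = 16.7 percentage points to a dose-level rate;
- 1/48 = 2.1 points overall.

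**Step 3. One cohort as an example.** Take 6 active subjects: 1 positive before and after dosing, 1 newly positive. The written count gives 2/6 = 33.3%. Newly positive subjects over all dosed give 1/6 = 16.7%; over pre-dose negatives, 1/5 = 20.0%. The denominator matters as well as the numerator.

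**Step 4. Chance that the problem arises.** Human pre-dose positivity p is not in the documents. I assume 1% to 10%. The chance of at least one pre-dose positive among n subjects is 1 − (1 − p)^n.

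**Step 5. Reported rate.** If pre-dose positives stay positive and a proportion q of the pre-dose negatives become positive, the written count has expected rate p + (1 − p)q.

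| Assumed p | ≥1 in a group of 6 | ≥1 among 48 | Reported rate if q = 0% | Reported rate if q = 10% |
|---|---|---|---|---|
| 1% | 5.9% | 38.3% | 1.0% | 10.9% |
| 2% | 11.4% | 62.1% | 2.0% | 11.8% |
| 5% | 26.5% | 91.5% | 5.0% | 14.5% |
| 10% | 46.9% | 99.4% | 10.0% | 19.0% |

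For example, at p = 10%: 1 − 0.90^6 = 0.469, and 0.10 + 0.90 × 0.10 = 0.19. At p = 0 every excess is zero.

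**The case against.** **The endpoint summary is promised separately.** A reader might infer that the SAP has chosen a rule that contradicts its endpoint. The documents do not go that far. Section 10 opens by promising a summary of subjects who develop ADA and NAb, and the at-least-one-positive table is described as an additional output. What stands is that the promised summary has no algorithm, and the only algorithm in the section has no pre-dose condition.

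**Pre-dose positives can be found.** By-visit counts, by-visit titers and the listings should show them, if pre-dose is tabulated as a visit. This softens the effect. It does not define the endpoint or settle who is ADA-positive in the TEAE table.

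**The animal data do not give a rate.** It is tempting to take prevalence from Protocol 5.2.3. In rats 5 of 219 samples (2.3%) were positive, and the protocol notes: "Three of them belong to the control group and the remaining positive samples were collected at pre-test". That is a rate per sample, at the screening tier, with signals near the cut-point. Only two of the five were pre-test, and the number of pre-test samples is not given. The vehicle monkeys (1/10 at Week 4, 1/4 at Week 8 in Table 4) were positive on study, not before dosing, and a pre-dose condition would not remove a new background positive. These data show that positives occur without exposure; they should not be used as human estimates.

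**No causal claim is made.** A reader might also infer that the plan attributes pre-existing reactivity to NS101. It does not. The immunogenicity summaries are descriptive and carry no statement of cause.

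**Any-positive status suits the PK table.** Protocol 13.5 specifies that category, and any antibody, old or new, might affect exposure. That choice is defensible. What remains open is whether pre-dose samples count.

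**Conclusion.** The point holds as a definitional gap with a concrete consequence. 'Develop' is undefined, and the only written subject-level count, followed literally, includes anyone positive both before and after dosing. In the PK-by-ADA summaries even a subject positive only before dosing could be classed as ADA-positive.

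The size depends on a quantity the documents do not give. It is zero if no subject is positive pre-dose. Otherwise it is 16.7 points per persistent pre-dose positive at dose level and 2.1 points overall. The 6% to 47% chance of at least one such subject in a six-subject group rests wholly on the assumed 1% to 10% prevalence. The per-subject and expected-rate figures also assume that pre-dose positives test positive again after dosing, and that all 48 active subjects are evaluable with no replacements.

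This is a descriptive secondary endpoint, and the planned by-visit output gives partial protection. The gap should be closed before the results are unblinded, but it does not threaten the primary safety objective.

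**What to change.** In SAP section 10:

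1. Define treatment-emergent ADA as either induced (pre-dose negative with at least one confirmed post-dose positive) or boosted (pre-dose positive with a post-dose titer rise above a prespecified fold, tied to the assay's validated variability).
2. Define emergent NAb from the pre-dose result in the same way. NAb is run only on confirmed ADA-positive samples, so state that a subject who is ADA-negative pre-dose counts as NAb-negative at baseline. The SAP reports NAb only as positive or negative, so without a NAb titer only the induced form applies.
3. State the denominator for each rate, and how a subject with a missing pre-dose sample is handled.
4. Use this definition for the 'develop' incidence and for the TEAE-by-ADA table. Report pre-dose positives separately, by dose level.
5. For PK-by-ADA and the boxplots, keep the protocol's any-positive category if wanted, but say whether pre-dose samples count, and add the treatment-emergent split.

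The cost is a few sentences of SAP text, a derived flag and the table shells that use it. The pre-dose sample is already scheduled. Keeping the any-positive PK category avoids a departure from Protocol 13.5; replacing it outright would need to be recorded in SAP section 12, which currently lists no changes.
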